### 9.3.1 Analysis of Primary Efficacy Endpoint

Not applicable since efficacy is not a primary objective.

## 9.3.2 Analysis of Secondary Efficacy and Pharmacodynamic Endpoint

### 9.3.2.1 Definition of Variables

Percent predicted forced expiratory volume in 1 second (ppFEV1): Percent predicted FEV1 is the ratio of FEV1 (L) and predicted FEV1 (L), expressed as a percentage. See Section 12.6 for more details.

Sweat chloride (SwCl): the SwCl value for a given visit will be calculated as the mean of the non-missing sweat chloride measurements obtained on the left and right arms at that visit. If one of the two arm measurements at a time point is missing, the other will be used as the mean. A volume  $\geq 15$   $\mu\text{L}$  is required for an accurate determination of sweat chloride. Any results reported as having volume  $< 15$   $\mu\text{L}$  will be considered missing. Any sweat chloride values reported as  $< 10$  mmol/L or  $> 160$  mmol/L will be considered missing.

Pulmonary exacerbation (PEX): A PEX is defined as a new event or change in antibiotic therapy (IV, inhaled, or oral) for any 4 or more of the following signs/symptoms:

- Change in sputum
- New or increased hemoptysis
- Increased cough
- Increased dyspnea
- Malaise, fatigue, or lethargy
- Temperature above 38°C (equivalent to approximately 100.4°F)
- Anorexia or weight loss
- Sinus pain or tenderness
- Change in sinus discharge
- Change in physical examination (PE) of the chest
- Decrease in pulmonary function by 10%
- Radiographic changes indicative of pulmonary infection

The number of PEX is then defined as the total number of PEX for each treatment group during the cumulative TC Efficacy period.

The time to first PEX is the number of days from the start of the cumulative TC Efficacy period to the date of the first pulmonary exacerbation during the cumulative TC Efficacy period. A subject who does not experience a PEX during the cumulative TC Efficacy period will be censored at the cumulative TC Efficacy period end date.

Body mass index (BMI): the BMI at each visit is calculated using the weight and height at each visit as follows:

$$\text{BMI} = \frac{\text{Weight (kg)}}{\text{Height}^2 (\text{m}^2)}$$

BMI z-score: the BMI score, adjusted for age and sex, will be referred to as BMI-for-age z-score (BMI z-score). The BMI z-score will be calculated by using Centers for Disease Control and Prevention (CDC) growth charts, with the age (in months) used for the calculation defined in Section 12.1.

Cystic Fibrosis Questionnaire-Revised (CFQ-R): The CFQ-R is a validated CF-specific instrument that measures quality-of-life domains. This study utilizes three different versions of CFQ-R:

- CFQ-R for Children ages 12 and 13
- CFQ-R for Adolescents and Adults (subjects 14 years and older)
- CFQ-R for Parents/Caregivers (subjects 13 years and younger)

In all three versions, specific question belonging to a domain is scored 1, 2, 3, or 4. The CFQ-R domain score, e.g., physical domain score or respiratory domain score, is defined as a scaled score as follows:

Scaled score for a domain =  $100 \times (\text{mean (scores of all questions in the domain)} - 1)/3$ , where the score from a negatively phrased question is first reversed, i.e., reversed score =  $5 - \text{actual score}$ , so that 1 always represents the worst condition and 4 the best condition. The (scaled) domain score ranges from 0 (worst condition) to 100 (best condition). The scaled score for a specific domain will not be calculated if more than half of the questions in the domain have missing scores.

The (scaled) domain score from the CFQ-R for Children ages 12 and 13 and for Adolescent and Adults will be pooled within and across subjects for the analysis purpose.

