### **3 INTRODUCTION**

This statistical analysis plan (SAP) for the interim and final analysis of Study 105 is based on the most recent approved clinical study protocol (CSP), the most recent approved electronic case report form (eCRF), and the most recent approved eCRF completion guidelines.

The SAP (Methods) Version 1.0, dated 31 January 2019, documented the planned statistical analyses and data presentations of safety and efficacy endpoints during Study 105 for subjects who previously participated in Study VX17-659-102 (Study 102), or Study VX17-659-103 (Study 103), and subsequently enrolled in Study 105. Due to the decision to end Study 105 early, the SAP has been amended to remove analyses that can no longer be conducted due to the early termination.

The Vertex Biometrics Department will perform the statistical analysis described in this document; SAS (Version 9.4 or higher) will be used to generate all statistical outputs (tables, figures, listings, and datasets).

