### 8.2 Cumulative TC Efficacy Period

For subjects who enrolled in the OLS, the time from the first dose of study drug in study 102 or study 103 (for subjects randomized to VX-659/TEZ/IVA in these studies) or in study 105 (for subjects not randomized to VX-659/TEZ/IVA in these studies) until the last efficacy assessment, which may be collected up to the Week 96 Visit or the earlier of Day 673 and the end of study participation if subject does not have the Week 96 Visit. For subjects who did not enroll in the OLS and were randomized to VX-659/TEZ/IVA in studies 102 or 103 and received study drug in the parent study, definition of this analysis period is the same as the parent study efficacy period. The cumulative TC Efficacy period for subjects from studies 102 and 103 who enrolled in the OLS is represented by the shaded portion in [Figure 8-1](#). The cumulative TC Efficacy period will be used with the cumulative TC Efficacy set for analysis of PEx data. Note that the data between SFUV of parent study and OLS informed consent form signing will not be collected when there is a gap in time between these two milestones; the corresponding duration will be excluded from the cumulative TC Efficacy period.

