### **9.2.5 Study Drug Exposure**

Duration of study drug exposure is defined as [last dose date – first dose date + 1 day] within the OL safety period, regardless of any interruption in dosing between the first and the last dose. For the IA, for subjects who are still on study drug at the IA data cutoff date, the IA data cutoff date will be used as the last dose date for the exposure calculation.

Study drug exposure (in weeks) during the OL safety period for the OL-SS will be summarized descriptively by the number of subjects (n), mean, SD, median, min, and max. It will also be summarized into the following categories:  $\leq 24$  weeks,  $>24$  to  $\leq 48$  weeks,  $>48$  to  $\leq 72$  weeks,  $>72$  to  $\leq 96$  weeks,  $>96$  weeks. Additionally, the total study drug exposure, defined as the sum total of the study drug exposure across all subjects (in patient-weeks and patient-years), will be provided. The summary will be by “Any VX-659/TEZ/IVA” group.

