### **9.3.2.2 Analysis Method**

For ppFEV1, sweat chloride, BMI, BMI z-score, body weight, and CFQ-R respiratory domain score, the raw value and change from parent study baseline will be summarized for each visit during the OL efficacy period for the OL-FAS.

The number of PEx during the cumulative TC Efficacy Period will be summarized for the cumulative TC Efficacy Set, by treatment group and overall for subjects from Study 102 and by overall for subjects in Study 103. In addition, the total number of PEx, PEx requiring hospitalization, PEx requiring IV antibiotic therapy, and PEx requiring hospitalization or IV antibiotic therapy will be summarized similarly.

[figure not shown]

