Summaries will be presented by MedDRA SOC and PT using frequency counts and percentages (i.e., number and percentage of subjects with an event) and the exposure adjusted event rate (except for summary by strongest relationship and maximum severity). When summarizing the number and percentages of subjects, subjects with multiple occurrences of the same adverse event will be counted once, and only the maximum severity level will be presented in the severity summaries, and the strongest relationship level in the relationship summaries. Missing severity levels will not be included in the Grade 3/4 TEAE summaries; missing relationship will be considered as related and included in the related TEAE and related serious TEAE summaries.

All AEs in study 105 database, including pretreatment AEs, TEAEs, and post-treatment AEs, will be presented in an individual subject data listing based on the OL All Subjects Set. In addition, a listing containing individual subject adverse event data for TEAEs leading to treatment discontinuation, TEAEs leading to treatment interruption, Grade 3/4 TEAEs, SAEs and all deaths will be provided separately, with a flag indicating the TEAE status for SAEs and deaths.

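### Pulmonary exacerbation counts are totalled over follow-up that differs by parent arm and by subject, with no person-time or rate planned

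*SAP*

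**What the plan says.** - **Definition of the count.** SAP 9.3.2.1: "The number of PEX is then defined as the total number of PEX for each treatment group during the cumulative TC Efficacy period".
- **Summary.** SAP 9.3.2.2 presents the count "by treatment group and overall for subjects from Study 102 and by overall for subjects in Study 103". It then adds the total number of PEx and three subtypes (hospitalization, IV antibiotics, either), summarized in the same way. Neither paragraph mentions follow-up time or a rate.
- **Period.** SAP 8.2 starts the clock at the first parent-study dose for subjects randomized to TC, "or in study 105 (for subjects not randomized to VX-659/TEZ/IVA in these studies) until the last efficacy assessment". TC-randomized subjects who did not enter Study 105 contribute their parent-study efficacy period alone. Where there is an uncollected gap between the parent study's safety follow-up visit and consent to Study 105, "the corresponding duration will be excluded from the cumulative TC Efficacy period".
- **Models.** Protocol 12.3.3.2 planned a negative binomial regression for the number of PEx and a Kaplan-Meier display for time to first PEx. SAP 9.3 now excludes negative binomial, Poisson and time-to-event analyses. SAP section 3 explains that "the SAP has been amended to remove analyses that can no longer be conducted due to the early termination". The time-to-first-PEx definition survives in 9.3.2.1, where event-free subjects "will be censored at the cumulative TC Efficacy period end date", but 9.3.2.2 plans no output for it.
- **Person-time elsewhere.** SAP 9.2.5: "Study drug exposure (in weeks) during the OL safety period for the OL-SS will be summarized descriptively", with total patient-weeks and patient-years for the pooled group. SAP 9.4.1 presents treatment-emergent AEs "using frequency counts and percentages (i.e., number and percentage of subjects with an event) and the exposure adjusted event rate".

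**The concern.** A total number of events has meaning only against the time over which events could occur. Here that time is unequal by construction. In Study 102 the former-TC column accrues parent-study plus open-label time, while the former-placebo column accrues open-label time only. Within each column it also varies with rollover, the gap exclusion and the early end of Study 105.

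Two consequences follow. The two Study 102 columns can show different totals when subjects have exacerbations at the same rate on TC. The overall totals for Studies 102 and 103 do not show how often PEx occur on long-term TC, which is what the secondary endpoint and the long-term efficacy objective ask. The protocol's negative binomial and Kaplan-Meier analyses, the natural places to account for follow-up time, have been removed, and nothing visible replaces them.

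The by-arm point concerns Study 102 only, because Study 103 is shown overall only.

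**Working it through.** **1. The plan's own PEx figure.** SAP 6.2 (and Protocol 12.1) states a 95% CI half-width below 6% for a PEx incidence of 30% with over 400 subjects. With n = 400: 1.96 × √(0.30 × 0.70 / 400) = 4.49%. The statement reproduces and is not in dispute. It concerns a cumulative incidence, not the event total that 9.3.2.1 defines.

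**2. Could another planned output serve as the denominator?**

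| Output | Period | Population and split |
|---|---|---|
| PEx totals (9.3.2.2) | cumulative TC Efficacy period | Cumulative TC Efficacy Set; Study 102 by arm and overall, Study 103 overall |
| Exposure (9.2.5) | OL safety period | OL-SS, pooled |
| Exposure-adjusted AE rates (9.4.1) | OL safety period | OL-SS, pooled |

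The last two omit parent-study time on TC, omit TC subjects who never entered Study 105, use the safety period instead of the efficacy period, and are not split by parent study or arm. They cannot be divided into the PEx totals.

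**3. Effect on the two Study 102 totals.** Let P be parent-study weeks on TC and T be mean open-label weeks. Assume equal arms, full rollover and a common rate r per week. The expected totals are n·r·(P+T) for former-TC subjects and n·r·T for former-placebo subjects, so their ratio is (P+T)/T. The documents give neither P nor the T achieved; SAP 8.2 limits T to about 96 weeks (Week 96 Visit or Day 673). Over assumed ranges:

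| P (weeks) | T = 24 | T = 48 | T = 72 | T = 96 |
|---|---|---|---|---|
| 4 | 1.17 | 1.08 | 1.06 | 1.04 |
| 12 | 1.50 | 1.25 | 1.17 | 1.13 |
| 24 | 2.00 | 1.50 | 1.33 | 1.25 |

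Under these assumptions the ratio for a given P is smallest at T = 96, and shorter follow-up raises it.

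**4. In events.** Read the 30% planning figure, as an assumption, as a 24-week incidence at a constant rate:

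- r = −ln(0.70)/24 = 0.01486 per week
- × 365.25/7 weeks per year = 0.775 per patient-year

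For 100 subjects per arm and P = 12:

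| T (weeks) | Former placebo: PEx (patient-years) | Former TC: PEx (patient-years) | Overall PEx, 200 subjects |
|---|---|---|---|
| 24 | 35.7 (46.0) | 53.5 (69.0) | 89.2 |
| 96 | 142.7 (184.0) | 160.5 (207.0) | 303.2 |

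Each total divided by its own patient-years returns 0.775 (for example 53.5/69.0). The rate is the same in every cell, and the differences in totals come only from follow-up.

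**The case against.** The strongest reply is that little rests on these totals. They are descriptive, the endpoint is secondary, there is no test or multiplicity scheme, and the SAP does not propose comparing the two Study 102 columns. The unequal periods are disclosed in SAP 8.2 and Figure 8-1. All of this is true, and it limits the consequence to interpretation; no error rate is affected. But disclosing unequal periods does not put the totals on a common scale, and the overall totals lack a time base whether or not anyone compares columns.

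A second reply is that the larger ratios need short follow-up. SAP Version 1.0 is dated 31 January 2019, and the COVID-19 addendum of 29 July 2020 still lists the study as ongoing, so T may have been long for some subjects. This does not establish the mean, but at T = 96 the ratio is only 1.04 to 1.25. Unequal arm sizes or incomplete rollover could also move the ratio either way, even below 1. Both points stand as limits on the size. They also show that the totals cannot be interpreted without the denominators.

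Third, parts of the SAP are redacted, so the absence of a rate can be asserted only for the visible text. The visible PEx definition, period and method paragraphs nevertheless read as complete. The SAP names exposure-adjusted rates explicitly for AEs, so its silence for PEx cannot be taken to imply one.

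Finally, early termination explains dropping the regression models. It does not explain omitting events divided by patient-years, which needs no model.

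**Conclusion.** The concern holds. As written, the PEx summary gives event totals over unequal follow-up with no denominator, and no other visible output supplies one. With equal arms, full rollover and identical true rates, the Study 102 totals would differ by a factor of 1.04 to 2.00 for P of 4 to 24 weeks and T of 24 to 96 weeks. P, T and the constant event rate are assumptions, so the range shows how large the effect could be and does not estimate it. The totals remain valid as counts, and the problem is confined to one descriptive secondary endpoint. It should be fixed because the stated method cannot show PEx frequency on long-term TC and the remedy is small.

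**What to change.** In SAP 9.3.2.1 and 9.3.2.2, add two descriptive items beside the PEx counts:

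1. Total patient-years in the cumulative TC Efficacy period, with the gap exclusion of SAP 8.2 applied and the year length defined (for example 365.25 days).
2. The crude PEx rate per patient-year: total events divided by total patient-years.

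Show both by parent treatment group and overall for Study 102, and overall for Study 103. Give the rate also for PEx requiring hospitalization, IV antibiotics, or either; these use the same denominator. Add a footnote that the columns are descriptive and not a randomized comparison. A confidence interval is optional and no regression is needed. If less is wanted, patient-years beside the counts is the minimum that lets a reader compute the rates.

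The cost is a short addition to two SAP paragraphs and a few rows or columns in one table. No new data are required, because SAP 8.2 and 9.3.2.1 already define the events, the period start and end, and the gap exclusion.

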### **9.3.2.2 Analysis Method**

For ppFEV1, sweat chloride, BMI, BMI z-score, body weight, and CFQ-R respiratory domain score, the raw value and change from parent study baseline will be summarized for each visit during the OL efficacy period for the OL-FAS.

The number of PEx during the cumulative TC Efficacy Period will be summarized for the cumulative TC Efficacy Set, by treatment group and overall for subjects from Study 102 and by overall for subjects in Study 103. In addition, the total number of PEx, PEx requiring hospitalization, PEx requiring IV antibiotic therapy, and PEx requiring hospitalization or IV antibiotic therapy will be summarized similarly.

[figure not shown]
### **9.3.2.3 Sensitivity and Supportive Analysis of Secondary Endpoints**

No sensitivity or supportive analysis is planned for the secondary endpoints.

### **9.3.2.4 Subgroup Analysis**

Not any.

#### **9.4 Safety Analysis**

The primary objective of study 105 is the evaluation of the long-term safety and tolerability of VX-659/TEZ/IVA. All safety analyses for study 105 will be based on the OL safety period for subjects in the OL-SS.

The following safety and tolerability endpoints will be assessed:

- Treatment-emergent adverse events (TEAEs)
- Clinical laboratory values
- ECGs

- Vital signs
- Pulse oximetry

The safety analysis will be performed by pooling the safety data from patients with parent studies 102 and 103.

The TC safety baseline will be used to calculate change from baseline for continuous safety endpoints.

In the AE summary tables, AE data from the OLS safety period may be displayed side-by-side with the AE data from study 102.

Only descriptive analysis of safety will be performed and no statistical testing will be performed.

#### **9.4.1 Adverse Events**

AEs will be classified as pretreatment AEs, TEAEs, or post-treatment AEs, defined as follows:

**Pretreatment AE:** any AE that occurred prior to the start of the OL safety period

**TEAE:** any AE that worsened (either in severity or seriousness) or newly developed during the OL safety period

**Post-treatment AE:** any AE that worsened (either in severity or seriousness) or that was newly developed after the OL safety period

For AEs in the study 105 database with completely missing or partially missing start dates, if there is no clear evidence that the AEs started before the OL safety period or after the OL safety period, the AEs will be classified as TEAEs.

Details for imputing missing or partial start dates of adverse events are described in Section [12.3](#).

An overview of all TEAEs during OL safety period will be summarized and include the following categories:

[figure not shown]
- Number of TEAEs (total number of TEAEs only)
- Subjects with any TEAEs
- Subjects with TEAEs by strongest relationship
- Subjects with TEAEs by maximum severity
- Subjects with TEAEs leading to study drug discontinuation
- Subjects with TEAEs leading to study drug interruption
- Subjects with Grade 3/4 TEAEs
- Subjects with related TEAEs
- Subjects with serious TEAEs
- Subjects with related serious TEAEs
- Subjects with TEAE leading to death

The frequency counts and percentages as well as the exposure adjusted event rate will be presented for the above overview table. The exposure adjusted rate will not be presented for strongest relationship and maximum severity categories.

The following summary tables of TEAEs during OL safety period will be presented:

- All TEAEs
- Grade 3/4 TEAEs
- TEAEs by strongest relationship
- TEAEs by maximum severity
- TEAEs leading to treatment discontinuation
- TEAEs leading to treatment interruption
- Related TEAEs
- Serious TEAEs
- Related serious TEAEs
- TEAEs leading to death

Summaries will be presented by MedDRA SOC and PT using frequency counts and percentages (i.e., number and percentage of subjects with an event) and the exposure adjusted event rate (except for summary by strongest relationship and maximum severity). When summarizing the number and percentages of subjects, subjects with multiple occurrences of the same adverse event will be counted once, and only the maximum severity level will be presented in the severity summaries, and the strongest relationship level in the relationship summaries. Missing severity levels will not be included in the Grade 3/4 TEAE summaries; missing relationship will be considered as related and included in the related TEAE and related serious TEAE summaries.

All AEs in study 105 database, including pretreatment AEs, TEAEs, and post-treatment AEs, will be presented in an individual subject data listing based on the OL All Subjects Set. In addition, a listing containing individual subject adverse event data for TEAEs leading to treatment discontinuation, TEAEs leading to treatment interruption, Grade 3/4 TEAEs, SAEs and all deaths will be provided separately, with a flag indicating the TEAE status for SAEs and deaths.

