12.3.4.1 Adverse Events

For analysis purposes, AEs will be classified as pretreatment AEs, TEAEs, or post-treatment AEs, defined as follows:

- **Pretreatment AE:** any AE that occurred since the end of the TE Period in the parent study and before the first dose of study drug in the TE Period in the open-label study
- **TEAE:** any AE that worsened (either in severity or seriousness) or newly developed at or after the first dose date of study drug in the TE Period in the open-label study
- **Post-treatment AE:** any AE that worsened (either in severity or seriousness) or newly developed after the TE Period in the open-label study

For AEs with missing or partial start dates, if there is no clear evidence that the AEs started before or after study drug treatment, then the AEs will be classified as TEAEs.

AE summary tables will be presented for TEAEs only and will include the following:

- All TEAEs
- TEAEs by strongest relationship
- TEAEs by maximum severity
- TEAEs leading to treatment discontinuation
- TEAEs leading to treatment interruption
- Serious TEAEs
- TEAEs leading to death
- Grade 3 and Grade 4 TEAEs
- Frequently reported TEAEs

Summaries will be presented by MedDRA SOC and PT using frequency counts and percentages (i.e., number and percentage of subjects with an event). When summarizing the number and percentage of subjects with an event, subjects with multiple occurrences of the same AE or a continuing AE will be counted once, only the maximum severity level will be presented in the severity summaries, and the strongest relationship level in the relationship summaries. An AE overview table will be provided. In addition, a listing containing individual subject level AE data for all deaths and other serious and significant AEs will be provided separately. All AEs, including pre- and post-treatment AEs, will be presented in individual subject data listings.

Exposure-adjusted event rates may also be provided.

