### 8.1 Open Label (OL) Period

**OL Efficacy Period:** Time from the first dose of study drug in the OLS until the last efficacy assessment, which may be collected up to the Week 96 Visit or the earlier of Day 673 and the end of study participation if subject does not have the Week 96 Visit. This analysis period will be used with the OL-FAS to analyze efficacy data during the OLS.

**OL Safety Period:** The time from the first dose of study drug in the OLS to 28 days after the last dose date of the study drug in the OLS or to the completion date of study participation (Section 9.1.5 of the study 105 CSP), whichever occurs first. This analysis period will be used with the OL-SS to analyze the safety data during the OLS.

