### **9.2.1 Subject Disposition**

A summary table of subject disposition in the OLS will be presented for the OL All Subjects Set by treatment group in the parent studies and overall with the following categories:

- Enrolled (OL All Subjects Set)
- Dosed (OL-SS)
- Enrolled and dosed (OL-FAS)

The number and percentage (based on OL-FAS) of subjects in each of the following disposition categories will be summarized by treatment group in parent studies and overall:

- Completed Treatment
- Prematurely discontinued treatment and the reasons for discontinuation
- Completed study
- Prematurely discontinued the study and the reasons for discontinuation

A listing will be provided for subjects who discontinued treatment during OLS or who discontinued OLS with reasons for discontinuation.

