### 12.3 Imputation Rules for Missing AE dates

Imputation rules for missing or partial AE start date in study 105 database are defined below. If the imputed AE start date is before the informed consent date for the OLS, the AE start date will be imputed using the informed consent date. Ongoing events from the parent studies will follow the imputation rule described in the SAP for parent studies.

- **If only Day of AE start date is missing:**

- If the full (or partial) AE end date is NOT before the first dose date of the OLS or AE end date is missing, then
  - if AE start year and month are equal to the month and year of first dose date of the OLS, then impute the AE start day as the day of first dose date of the OLS;
  - else impute the AE start day as 1.
- else impute the AE start day as 1.

Compare the imputed AE start date with TE period to determine whether the AE is pretreatment AE, TEAE or post-treatment AE.

- **If Day and Month of AE start date are missing:**

- If the full (or partial) AE end date is NOT before the first dose date of the OLS or AE end date is missing, then
  - if AE start year is equal to the year of first dose date of the OLS, then impute the AE start month and day as the month and day of first dose date of the OLS;
  - else impute the AE start month as January and day as 1.
- else impute the AE start month as January and day as 1.

Compare the imputed AE start date with TE period to determine whether the AE is pretreatment AE, TEAE or post-treatment AE.

- **If Year of AE start date is missing:**

If the year of AE start is missing or AE start date is completely missing then query site.

- If the full (or partial) AE end date is NOT before the first dose date of the Treatment Period or AE end date is missing, then impute the AE start date as the first dose date of the OLS.
- else impute the AE start date as the informed consent date.

Imputation rules for partial AE end date in study 105 database are defined below:

If partial end date, then impute as min (the last day of the month, data cut-off for IA, end of study) if day is missing, or min (Dec, data cut-off for IA, end of study) if month is missing.

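### AEs that began before the first open-label dose, do not worsen, but lead to stopping or interrupting drug in Study 105 fall outside every discontinuation and interruption AE table

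*SAP*

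**What the plan says.** SAP 9.4.1 sorts AEs by timing. A TEAE is "any AE that worsened (either in severity or seriousness) or newly developed during the OL safety period"; a pretreatment AE is "any AE that occurred prior to the start of the OL safety period". SAP 8.1 defines that period as "The time from the first dose of study drug in the OLS to 28 days after the last dose date of the study drug"; it ends sooner if study participation ends first. Parent-study treatment does not move its start.

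The overview table has the row "Subjects with TEAEs leading to study drug discontinuation" and a matching row for interruption. The SOC/PT tables carry the same restriction. Protocol 12.3.4.1 says AE summary tables are for TEAEs only, and its list includes "TEAEs leading to treatment discontinuation".

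The focused listing covers "TEAEs leading to treatment discontinuation, TEAEs leading to treatment interruption, Grade 3/4 TEAEs, SAEs and all deaths will be provided separately"; in it, SAEs and deaths are flagged for TEAE status. A second listing holds every AE in the Study 105 database, pretreatment AEs included.

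The disposition table in SAP 9.2.1 has the category "Prematurely discontinued treatment and the reasons for discontinuation", without a TEAE restriction and with a supporting listing. SAP 12.3 foresees AEs carried over: "Ongoing events from the parent studies will follow the imputation rule described in the SAP for parent studies".

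**The concern.** The primary objective is long-term safety and tolerability, and stopping or interrupting drug because of an AE is one of its most direct measures. In a rollover study an AE can begin before the first open-label dose and lead to action on study drug only afterwards. If the AE has not become more severe or serious, nothing in the definitions turns that later action into a TEAE, so the subject is absent from the tables a reader would consult for AE-related stops and interruptions.

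For a subject already on TC in the parent study, such an event bears on how well TC is tolerated over time. The omission works in one direction, because it can only reduce the counts. SAP 9.4 also allows the open-label AE data to be shown beside Study 102, where an undercount in one column could mislead.

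**Working it through.** **1. Trace one case through the outputs.** Take an AE with onset before the first open-label dose and no later change in severity or seriousness, with drug withdrawn or interrupted in Study 105.

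| Output | Limited to TEAEs? | Shows the case? |
|---|---|---|
| Overview rows for discontinuation and interruption (SAP 9.4.1) | Yes | No |
| SOC/PT tables for discontinuation and interruption (SAP 9.4.1) | Yes | No |
| Focused listing, discontinuation and interruption entries | Yes | No |
| Focused listing, SAEs and deaths | No, flagged | Only if serious |
| All-AE listing | No | Yes, if in the Study 105 database |
| Disposition table and listing (SAP 9.2.1) | No | Discontinuations only, by reason, no SOC/PT |
| Compliance summary (SAP 9.2.6) | No | Interruption days only, no cause |

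So a discontinuation keeps one summary count, and an interruption keeps none that links it to an AE.

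**2. Can the case occur?**
- Protocol 9.1.1 normally places Day 1 on the day of the last scheduled parent-study visit, so unresolved AEs pass straight through.
- Protocol 8.1 admits subjects who had drug interruptions in the parent study.
- Protocol 9.1.1 lets consent be signed up to 28 days before Day 1, and AEs are collected from consent (Protocol 13.1.1.3). Some pretreatment AEs therefore belong to Study 105's own collection.
- One interruption criterion in Protocol 9.8.1 depends on duration: ALT or AST above five times ULN for longer than two weeks. An elevation present before rollover and stable afterwards can meet it through elapsed time alone.

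**3. Compare with how the SAP treats other safety data.** For laboratory, ECG, vital-sign and oximetry data, SAP 9.1 uses a TC safety baseline that goes back before the first parent-study dose for subjects who received TC there. For AEs the clock restarts at rollover. SAEs and deaths enter the focused listing whatever their onset; discontinuations and interruptions do not.

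**4. Size.** Inputs: N = 400 (the documents expect over 400) and the precision statements in SAP 6.2. These reproduce:
- P(at least one event at a 1% rate) = 1 − 0.99^400 = 0.982.
- One-sided 95% upper bound with zero events = 1 − 0.05^(1/400) = 0.75%, below 1%.
- PEx half-width = 1.96 × √(0.3 × 0.7/400) = 4.5 points, below 6.

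Each subject left out lowers a percentage by 1/400 = 0.25 points. The documents give no count of affected subjects, so no corrected percentage can be derived. For illustration only, suppose the table shows c subjects and k are left out. The full figure is (c + k)/400 and the absent share is k/(c + k):

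| Shown c (assumed) | k = 1 | k = 2 |
|---|---|---|
| 4 (1.0%) | 1.25%, 20% absent | 1.5%, 33% absent |
| 8 (2.0%) | 2.25%, 11% absent | 2.5%, 20% absent |
| 12 (3.0%) | 3.25%, 8% absent | 3.5%, 14% absent |

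SAP 6.2 applies its zero-event statement to AE occurrence by PT. Applied by analogy to a PT row of the discontinuation table, a shown zero gives the 0.75% bound. If one subject was left out, the exact one-sided 95% bound is 1.18%, from (1 − p)^400 + 400p(1 − p)^399 = 0.05.

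**The case against.** **The SAP follows the protocol.** Protocol 12.3.4.1 limits AE summary tables to TEAEs, and Protocol 12.3.4 names TEAE incidence as a safety endpoint. This stands. It is why the remedy should be additional rows, declared as such, and not a redefinition of the planned tables.

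**For subjects from placebo or TEZ/IVA, the exclusion is intended.** An unchanged AE that began before any TC is what treatment-emergence is meant to keep out. This also stands. The tolerability argument is strongest for subjects with prior TC, so any added rows must be split by parent-study treatment.

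**Much of the information survives.** A reader might infer that every parent-onset AE leading to a stop is missed, or that discontinuations are hidden. Neither follows. A carried-over AE that worsens is a TEAE and is counted. Under Protocol 9.8.2, for example, a rash that newly reaches Grade 3 or becomes serious in Study 105 has worsened. All treatment discontinuations appear in the disposition table, and laboratory threshold events in SAP 9.4.2 do not depend on AE onset. What is lost is the SOC/PT attribution and the focused-listing entry for discontinuations, and any AE-linked summary for interruptions.

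**Recording is not fully documented.** SAP 12.3 concerns date imputation; it does not show how a later Study 105 drug action is entered against a parent-study AE. Protocol 13.1.1.2 counts discontinuation from the study among the criteria for a clinically significant abnormal assessment, which could prompt a new AE record, but it also requires worsening from baseline. This qualifies the cost estimate, not the gap in the tables.

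**Frequency is unknown.** Protocol 8.2 lets investigators exclude subjects with prior intolerance that would pose added risk, which may make such cases rare. This stands.

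**Conclusion.** The point holds for a defined group: AEs with onset before the first open-label dose, unchanged in severity and seriousness, that lead to drug being stopped or interrupted in Study 105. They are pretreatment AEs under SAP 9.4.1 and are absent from the TEAE discontinuation and interruption rows, the SOC/PT tables and, unless serious, the focused listing. The gap is clearest for interruptions.

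The effect is 0.25 percentage points per subject at N = 400, always downwards. The conclusion assumes that such AEs reach the Study 105 database, as SAP 12.3 implies.

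Two stronger readings are tempting and unsupported. A reader might infer that the parent study does not count the event either, so that it is lost from both studies. The parent-study SAPs are not among the documents, so this cannot be checked. A reader might also infer that the relative understatement is large. That depends on counts the documents do not give, and the table of assumed counts under the check shows only how sensitive a small count would be.

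**What to change.** Keep the TEAE tables unchanged. Then:

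1. In SAP 9.4.1, add supplementary rows for AEs with onset before the first open-label dose whose recorded action in the OL safety period is drug withdrawn or drug interrupted. Split them by parent-study treatment: prior TC versus placebo or TEZ/IVA.
2. Extend the focused listing to all AEs leading to discontinuation or interruption in the OL safety period, regardless of onset, with the TEAE flag already planned for SAEs and deaths.
3. Reconcile the number of subjects with an AE leading to discontinuation (TEAE plus supplementary row) with those whose disposition reason is an adverse event, and explain any difference. SAP 9.2 presents disposition separately for Studies 102 and 103, so the two must be added first.
4. State in the SAP that these rows are an addition to Protocol 12.3.4.1, which limits AE summary tables to TEAEs.

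The cost is SAP wording, a small programming change and a slightly less favourable count. Protocol 13.1.1.3 and 13.1.1.6 already provide for AE dates and action taken. Before programming, confirm that the action field is completed in Study 105 for AEs carried over from the parent study.
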